6.4 Handling of missing data

In principle, missing data will not be imputed. However, if missing data is imputed for analysis at the final evaluation time point, LOCF may be used.

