4.5 Withdrawal from study or discontinuation of administration

The principal investigator or sub-investigator will as far as possibly encourage subjects to complete the study, but subjects can withdraw for any reason. The principal investigator or sub-investigator will notify the sponsor about all discontinuations. If one or more of the following is applicable, the principal investigator or sub-investigator will discontinue study drug administration to the subject, and then discontinue the study. Note that the study will be considered completed when administrations and observations up to Visit 19 are completed.

- The principal investigator or sub-investigator judges discontinuation to be necessary due to one or more serious or intolerable adverse events.
- The principal investigator or sub-investigator judges that insufficient efficacy of the study drug has resulted in aggravation of the primary disease, making discontinuation necessary.
- Pregnancy of the subject.

- The subject or his/her legal representative expresses the wish to withdraw from the study.
- The ineligibility of the subject is revealed after registration.
- Administration of duloxetine at a dose of 40 mg/day or higher is difficult at or after Visit 3.
- The subject is unable to visit hospital due to moving home, transferring to a different hospital, etc.
- Death of the subject.
- It is judged that management of abnormal hepatic function test results is necessary, as is withdrawal on the basis of the discontinuation criteria (Appendix 2).
- Discontinuation is judged by the principal investigator or sub-investigator to be necessary for any other reason.

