6.3 Assessments, observations and tests: Permitted timing and handling in statistical analyses

In principle, data obtained at the time-points shown in the case report forms, and collected in accordance with the performance schedule shown in the study protocol, will be used for the statistical analysis. In the case of data reported at the discontinuation visit, the time-points for use in analyses will be determined on the basis of the permitted ranges in the performance schedule. If there is duplication by data obtained at the scheduled visits and data obtained at the discontinuation tests, the data obtained closest to the scheduled date will be used. If this does not eliminate duplication, data from the scheduled visit will be used. Unscheduled visits will not be included in the time-points for analysis. For the permitted ranges for the observation, test, and evaluation time-points shown in the study protocol, refer to Appendix 2.

For the final evaluation, data obtained at weeks 51 to 52 or at discontinuation of the treatment/tapering period will be used, except for CDRS-R and CGI-S scores, for which those obtained at week 50 or at discontinuation of the treatment period are used. However, if none of the above data are available, the latest data among reported data collected at scheduled visits are used for the final evaluation.

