9.1.1 Analysis of efficacy endpoints

The following analyses will be performed for the efficacy endpoints.

- 1) Analysis of CDRS-R total score, CGI-S, CDRS-R subscales, and item 13 (suicidal ideation)
 - A) Summary statistics will be calculated at each evaluation time-point in this study.
 - B) Summary statistics for changes from baseline in this study will be calculated at each evaluation time-point and the 95% confidence interval for the mean will be calculated.
 - C) Time-course graph for mean changes (standard deviation) from baseline will be prepared, where the baseline is Visit 2 of this study.
 - D) The CGI-S score category distribution will be summarized at baseline (Visit 2 of this study) and at the final evaluation (week 50 of administration or discontinuation of the treatment period).
- 2) Analysis of CDRS-R total score, CGI-S, CDRS-R subscales, and item 13 (suicidal ideation) from the initiation of the preceding study throughout this study

The following analyses will be performed only in consecutive subjects:

- A) Summary statistics will be calculated at each evaluation time-point in the preceding study and this study.
- B) Summary statistics for changes from baseline in the preceding study will be calculated at each evaluation time-point in the preceding study and this study and the 95% confidence interval for the mean will be calculated.
- C) Time-course graph for mean changes (standard deviation) from baseline in the preceding study will be prepared.
- D) The CGI-S score category distribution will be summarized at baseline in the preceding study and at the final evaluation (week 50 of administration or discontinuation of the treatment period).

10. Safety evaluation

Safety analyses will be performed with the safety-analysis set.

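### Week 50 efficacy means rest on subjects still observed, with no model or missing-data sensitivity analysis, although 25% dropout is planned and worsening is a listed reason to stop

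*SAP*

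**What the plan says.** - **By-visit summaries.** SAP 9.1.1 states: "Summary statistics for changes from baseline in this study will be calculated at each evaluation time-point", with a 95% confidence interval for the mean. Protocol 8.10 applies the summaries to observed values in the FAS.
- **Missing data.** SAP 6.4 begins: "In principle, missing data will not be imputed". It then says that "if missing data is imputed for analysis at the final evaluation time point, LOCF may be used". Protocol 8.4 has the same wording.
- **Final evaluation.** For CDRS-R and CGI-S, SAP 6.3 says "those obtained at week 50 or at discontinuation of the treatment period are used". It adds a fallback: "if none of the above data are available, the latest data among reported data collected at scheduled visits are used for the final evaluation". Neither sentence is optional.
- **Where the final evaluation is used.** SAP 9.1.1 names it only for the CGI-S category distribution. SAP 10.2 to 10.5 list it explicitly for the safety data.
- **Dropout.** SAP 4.3 and protocol 8.2 assume 25% dropout. Protocol 4.5 includes among ten reasons for discontinuing that "insufficient efficacy of the study drug has resulted in aggravation of the primary disease, making discontinuation necessary".
- **Status of efficacy.** It is a secondary objective. SAP section 9 calls the analysis mainly descriptive and specifies no efficacy test. It also gives no model and no sensitivity analysis for missing efficacy data.

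**The concern.** A by-visit mean over subjects still under observation describes a changing group. If those who leave are on average doing worse, part of the apparent improvement over 50 weeks comes from the group becoming more selected. The 95% confidence interval does not show this, because it reflects only sampling error around the mean of those who remain. The plan itself foresees dropout linked to the efficacy score, since worsening is a listed reason to stop.

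The other available summary is the final evaluation. It brings in subjects who left, but by their last value on treatment. The plan does not say whether CDRS-R total is reported on that basis, nor which of the two summaries is the main long-term result. At stake is how the long-term efficacy objective is read, not any error rate or the sample size.

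**Working it through.** **1. The plan's own figure.** 100 one-year completers and 25% dropout give 100 / (1 - 0.25) = 133.3, so 134. The stated 135 agrees closely, and 135 x 0.75 = 101.25 completers. About a quarter of registered subjects are therefore expected to lack a week 50 value on treatment.

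**2. Size of the bias.** Let d be the dropout share. Observed-case bias at week 50 = d x (completer mean change - dropout mean change). The documents give no CDRS-R mean, no SD and no share of dropout due to lack of efficacy, so the gap is an assumption. Overstatement of improvement, in CDRS-R points:

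| Dropouts improve less by | 0 | 5 | 10 | 15 | 20 |
|---|---|---|---|---|---|
| d = 0.25 | 0 | 1.25 | 2.5 | 3.75 | 5.0 |
| d = 0.10 | 0 | 0.5 | 1.0 | 1.5 | 2.0 |

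The second row covers the case where only part of the dropout is related to response.

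**3. Illustrative simulation.** Assumed: mean improvement 20 points, approached exponentially with an 8-week time constant; between-subject SD 12; residual SD 6; the protocol's visit weeks; dropout possible after week 4 and after each later visit, driven by the last observed change and tuned to 25% in total. Mean week 50 change (negative is improvement):

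| Dropout and response | True | Observed case | Last on treatment |
|---|---|---|---|
| Unrelated | -19.92 | -19.92 | -19.23 |
| Moderately related | -19.98 | -21.62 | -18.85 |
| Strongly related | -19.91 | -22.70 | -18.42 |
| Very strongly related | -19.94 | -23.41 | -18.12 |

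The observed-case mean overstates improvement by 0, 1.64, 2.79 and 3.47 points. The formula in step 2 agrees. In the last row dropouts would have changed by -9.5, and 0.25 x (-23.41 + 9.5) = -3.48. Measured against the mean had everyone continued, the last-on-treatment mean understates improvement by 0.69 to 1.82 points. The two summaries differ by 0.69 to 5.29 points.

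**4. What a likelihood estimate would do.** A second simulation (true change about -20, same SDs, n = 135) took three increasing levels of dependence on the last score. Observed-case means were -21.3, -22.6 and -23.3. LOCF means were -18.7, -18.7 and -18.5. A likelihood estimate with unstructured covariance gave -20.1, -20.2 and -20.0. With unrelated dropout, observed-case and likelihood were both -20.0. Dropout here depends only on observed scores, so missing at random holds by construction; this is the favourable case for the model.

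**5. Discontinuation scores.** SAP 6.3 assigns them to visits by the permitted ranges. In SAP Appendix 2 the post-baseline windows are three of 7 days (Visits 3, 4 and 17) and twelve of 15 days (Visits 5 to 16): 3 x 7 + 12 x 15 = 201 days. Of days 1 to 353, 353 - 201 = 152 (43%) lie in no window, for example days 36 to 48. A CDRS-R score taken at discontinuation on such a day may enter no by-visit mean. The 43% is a share of calendar days, not the probability that a score is lost, because stopping often coincides with a visit.

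**The case against.** The strongest case against has four parts.

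- **Direction.** A reader might infer that week 50 improvement is overstated. The documents do not support that as a statement of fact. The 25% is all-cause, and protocol 4.5 also lists adverse events, moving home, pregnancy and the subject's wish. If dropout is unrelated to response the bias is zero, and if recovered subjects leave it reverses. This part stands, and the point is conditional.
- **Late choice.** A reader might also infer that the sponsor can choose the final-evaluation method once results are visible in this open-label study. SAP 6.3 largely closes that: its last-on-treatment rule is fixed and is LOCF in effect. What remains is unreconciled wording between 6.3 and 6.4, and no stated final-evaluation output for CDRS-R.
- **Target.** Last-on-treatment values understate improvement only against a mean had everyone continued. The documents do not say that this is the quantity sought. For a while-on-treatment question, the discontinuation score is a legitimate observed value. This stands, so the final-evaluation summary should be kept.
- **Model burden and impact.** With 15 post-baseline visits an unstructured covariance has 15 x 16 / 2 = 120 parameters. Cohort-by-visit terms for an assumed three cohorts, plus baseline, add 3 x 15 + 1 = 46 fixed effects, with about 135 subjects. That is too heavy without a fallback. Efficacy is also descriptive and uncontrolled, and n and withdrawal reasons are already tabulated (SAP 6.1 and 7.1). Both limit the point's weight. Tabulating n and reasons shows how many left and why, but does not estimate the effect on the mean.

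**Conclusion.** The concern holds in conditional form. The planned week 50 means are observed-case, with planned attrition of 25% and a foreseen route for response-related dropout, and nothing in the plan gauges the effect. The illustrative overstatement is 0 to about 3.5 CDRS-R points for a true change near -20. The actual size depends on how much worse dropouts do, which the documents do not give.

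The LOCF sentence in SAP 6.4 is mainly a drafting inconsistency with 6.3, and it does not leave the efficacy result open to selection. No error rate, sample size or primary (safety) conclusion is affected. The change is worth making because it is cheap, uses data already scheduled at Visits 2 to 17, and reduces the bias if data are missing at random.

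**What to change.** 1. **SAP 9.1.1.** Beside the observed-case tables, add a likelihood-based repeated-measures model for change from this study's baseline in CDRS-R total and in CGI-S score. Include categorical visit, baseline score and cohort (new subjects; consecutive subjects by treatment group in the preceding study). Pre-specify a fallback covariance structure if the unstructured one does not converge, and state how cohorts are weighted in the overall mean. Report the week 50 adjusted mean with its 95% confidence interval.
2. **SAP 9.1.1.** Report CDRS-R total at week 50 (observed, with n) and at the 6.3 final evaluation side by side.
3. **SAP 6.4.** Replace the LOCF option with a reference to 6.3. Record this, with the reason, as a change from protocol 8.4, as protocol 8.1 requires.

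**Cost:** SAP wording, one model per endpoint and one extra table row; no new data collection. **Downside:** the model relies on missing at random, which cannot be verified from the data, and CGI-S is a seven-grade score treated as continuous.

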6.5 Baseline

Data obtained before initiation of study drug administration (Visit 2) in this study will be used as baseline data, unless otherwise specified. As with laboratory test results of new subjects, if data from Visit 2 are missing, data from Visit 1 (screening period) will be used as baseline data. The baseline for the analysis of

data from the preceding study throughout this study will be the observed values obtained before initiation of study drug administration in the preceding study.

7. Subject composition and backgrounds

7.1 Disposition of patients

With registered subjects, the number who complete the treatment period and the number of withdrawals are calculated, and in the case of the withdrawals the disposition of the reasons for discontinuation is shown. Among subjects transferred to the tapering period, the number who complete the tapering period and the number of withdrawals are calculated, and the disposition of the reasons for discontinuation is summarized.

7.1.1 Patient composition in efficacy evaluation

With registered subjects, the numbers of subjects included in and excluded from the FAS will be calculated, and the disposition of the reasons for exclusion will be shown.

7.1.2 Patient composition in safety evaluation

With registered subjects, the numbers of subjects included in and excluded from the safety-analysis set will be calculated, and the disposition of the reasons for exclusion will be shown.

7.2 Analysis of demographic factors

With the safety-analysis set, summary statistics will be determined for the following continuous data items; and the frequencies and proportions of subjects in each category will be determined for discrete values: For the consecutive subjects, each demographic factor will also be summarized by the treatment group in the preceding study. Demographic factors will also be calculated separately for new subjects.

Data type	Item
Continuous	Age on date of obtaining legal representative's informed consent, age at initial onset of depression, height, body weight, CDRS-R total score baseline value, CDRS-R subscale (mood, somatic, subjective, behavior) baseline values, CGI-S score baseline value
Discrete	Sex (male, female), ethnicity, race, age on date of obtaining legal representative's informed consent (<12, \geq 12), depressive episode ordinal number (first time, second time, third to seventh time, eighth time or more, not known), duration of current depressive episode (0 to 2 weeks, 2 to 4 weeks, 4 to 8 weeks, more than 8 weeks, not known), disease class according to DSM-5 (depression, persistent depressive disorder), hospitalization status category (hospitalized, out-patient), medical and surgical history (present, absent), complications (present, absent), previous drug treatment (present, absent), previous therapy (present, absent)

The dispositions of medical and surgical history, complications, previous drug treatment, and previous therapy will be shown. Drugs used previously will be coded for using the WHO Drug Dictionary, and summarized on the basis of consistently selected noncommercial names.

8. Treatment course and compliance

8.1 Compliance

8.1.1 Duration of administration and total dose

The following analyses will be performed for the administration in this study with the safety-analysis set:

- 1) Summary statistics for study drug administration duration will be calculated. Administration duration is defined as follows:

Administration duration (days)

$$= (\text{administration completion date}) - (\text{administration initiation date}) + 1.$$

In addition, times (days) will be converted to week units, and the distributions in the following categories will be summarized: 12 or less weeks; more than 12 to 24 weeks; more than 24 to 50 weeks; and more than 50 weeks.

- 2) Summary statistics will be calculated for the total dose of study drug.
- 3) For the maximum and final doses during the treatment period, the distribution in the following categories will be summarized: 20 mg, 40 mg, 60 mg, 80 mg, and 540 mg.

8.1.2 Compliance rate

In the safety-analysis set, summary statistics for compliance rate during the treatment period will be calculated. Distribution in the following categories will be summarized: less than 70%, and 70% or more.

Compliance rate is defined as follows:

$$\text{Compliance rate [%]} = \frac{\{ \text{Total Prescription} - 20 \times (\text{Total number of untaken capsules}) \}}{(\text{Total Prescription})} \times 100$$

8.2 Concomitant treatment

The following analyses will be performed with the safety-analysis set: Concomitant drugs will be coded for using the WHO Drug Dictionary, and then summarized on the basis of consistently selected noncommercial names.

- 1) The number and proportion of subjects who have taken any concomitant medication at least once during the study period will be calculated. In addition, the disposition of the concomitant medication(s) will be shown. If use of the same concomitant medication has been reported more than once with the same subject, this will be taken to be one concomitant medication.
- 2) The number and proportion of subjects who have had any concomitant therapy at least once during the study period will be calculated. In addition, the disposition will be shown by the name of concomitant therapy. If use of the same concomitant therapy has been reported more than once with the same subject, this will be taken to be one concomitant therapy.

9. Efficacy evaluation

Efficacy analyses will be performed with the FAS. Efficacy endpoints are summarized in Table 1. The statistical analysis will be mainly descriptive; when changes from the initiation of the preceding study or from the initiation of the open-label extension study are evaluated, the 95% confidence interval for the mean will be calculated.

Table 1. Summary of endpoints and analysis methods

	Observed values		Changes	
	Summary statistics	95% confidence interval for mean	Summary statistics	95% confidence interval for mean
CDRS-R total score.	○	○	○	○
CGI-S	○	○	○	○
CDRS-R subscales and item 13 (suicidal ideation)	○	○	○	○

○: to be calculated

9.1 Endpoints

1) CDRS-R total score.

The CDRS-R total score will be calculated by adding together the scores for answers to all questions in the 17 items (refer to Appendix 3).

2) CDRS-R subscales and item 13 (suicidal ideation)

The CDRS-R subscales are defined as mood, somatic, subjective and behavior (refer to Appendix 3).

3) CGI-S

Disease severity will be evaluated on the basis of seven grades, from 1 (no disease or abnormality) to 7 (extremely severe disease). The analysis of CGI-S will be based on the score.

9.1.1 Analysis of efficacy endpoints

The following analyses will be performed for the efficacy endpoints.

- 1) Analysis of CDRS-R total score, CGI-S, CDRS-R subscales, and item 13 (suicidal ideation)
 - A) Summary statistics will be calculated at each evaluation time-point in this study.
 - B) Summary statistics for changes from baseline in this study will be calculated at each evaluation time-point and the 95% confidence interval for the mean will be calculated.
 - C) Time-course graph for mean changes (standard deviation) from baseline will be prepared, where the baseline is Visit 2 of this study.
 - D) The CGI-S score category distribution will be summarized at baseline (Visit 2 of this study) and at the final evaluation (week 50 of administration or discontinuation of the treatment period).
- 2) Analysis of CDRS-R total score, CGI-S, CDRS-R subscales, and item 13 (suicidal ideation) from the initiation of the preceding study throughout this study

The following analyses will be performed only in consecutive subjects:

- A) Summary statistics will be calculated at each evaluation time-point in the preceding study and this study.
- B) Summary statistics for changes from baseline in the preceding study will be calculated at each evaluation time-point in the preceding study and this study and the 95% confidence interval for the mean will be calculated.
- C) Time-course graph for mean changes (standard deviation) from baseline in the preceding study will be prepared.
- D) The CGI-S score category distribution will be summarized at baseline in the preceding study and at the final evaluation (week 50 of administration or discontinuation of the treatment period).

10. Safety evaluation

Safety analyses will be performed with the safety-analysis set.

10.1 Adverse events and adverse drug reactions

Adverse events occurring at or after the initiation of the open-label extension study and continuing from the preceding study will be evaluated. Reported adverse events will be converted to Medical Dictionary for Regulatory Activities (MedDRA) terms, and tabulated by system organ class and preferred term.

- 1) The number of subjects with a given adverse event and the number of cases will be determined, and the incidence rate and 95% confidence interval will be calculated. The incidence rate will be obtained as the proportion of subjects in the analysis set with a specific adverse event, and the confidence interval for the incidence rate will be determined by the Clopper-Pearson method. Totaling will be performed in a similar manner to above with deaths, other serious adverse events, adverse events leading to administration discontinuation, adverse events leading to dose reduction, adverse drug reactions, deaths as adverse drug reactions, other serious adverse drug reactions, adverse drug reactions leading to administration discontinuation, and adverse drug reactions leading to dose reduction. The relevant definitions are shown below.

Death	Adverse event with “Death” as the outcome
Other serious adverse event	Adverse event in the seriousness category “Serious”, except for death
Adverse event leading to administration discontinuation	Adverse event for which the study drug action is “Administration discontinuation”
Adverse event leading to dose reduction	Adverse event for which the study drug action is “Dose reduction”
Adverse drug reaction	Adverse event with the causal relationship with the study drug judged to be other than “Not related”
Death as adverse drug reaction	Death, with the causal relationship with the study drug judged to be other than “Not related”
Other serious adverse drug reaction	Other serious adverse event with the causal relationship with the study drug judged to be other than “Not related”
Adverse drug reaction leading to administration discontinuation	Adverse event leading to administration discontinuation, with the causal relationship with the study drug judged to be other than “Not related”
Adverse drug reaction leading to dose reduction	Adverse event leading to dose reduction, with the causal relationship with the study drug judged to be other than “Not related”

- 2) The number of subjects with a given adverse event, the number of cases, and the incidence rate will be determined by adverse event system organ class and preferred term. However, when calculating the number of subjects with a given adverse event and the incidence rate, if the same adverse event occurs more than once with the same subject, these events will be taken to be have affected one subject. Adverse drug reactions will be tabulated similarly.
- 3) With respect to adverse events with an incidence of 2% or more, the number of subjects, number of cases, and incidence rate will be calculated for each adverse event preferred term. Adverse drug reactions will be tabulated similarly.
- 4) The number of subjects and incidence rate will be calculated for each severity and outcome category, by adverse event system organ class and preferred term. If the same adverse event occurs more than once in different categories with the same subject, it will be taken to have occurred once, in the category with the highest of the below priority ranks. Adverse drug reactions will be tabulated similarly.

Priority rank	Survey item category	
	Severity	Outcome
1	Severe	Death
2	Moderate	Recovery with sequelae
3	Mild	No improvement
4		Partial recovery
5		Recovery
6		Unknown

- 5) The number of subjects and the incidence rate will be calculated for each onset timing category (weeks 0 to 8; weeks 8 to 16, weeks 16 to 24, weeks 24 to 32; weeks 32 to 40; weeks 40 to 48; weeks 48 to 50; later than week 50) for adverse events during the treatment period, by system organ class and preferred term. The denominator of the incidence rate will be the number of subjects with administration duration no shorter than the lower limit of each onset time category. The onset timing will be calculated as follows:

Onset timing [day]

$$= (\text{onset date}) - (\text{administration initiation date in the open-label extension study}) + 1$$

When calculating the number of subjects and the incidence rate, if the same adverse event occurs in different categories more than once in the same subject, it will be taken to have occurred with one subject in each of the relevant categories. Adverse drug reactions will be tabulated similarly.

- 6) With subjects in the safety analysis set who are transferred to the tapering period, adverse events that occur during the tapering period will be summarized. The number of subjects with a given adverse event, the number of cases, and the incidence rate will be determined by adverse event system organ class and preferred term. However, when calculating the number of subjects with a given adverse event and the incidence rate, if the same adverse event occurs more than once with the same subject, these events will be taken to be have affected one subject. Adverse drug reactions will be tabulated similarly.
- 7) With respect to adverse events for which the following standard MedDRA queries (SMQ) are applicable, the number of subjects, number of cases, and incidence rate will be determined by system organ class and preferred term. However, when calculating the number of subjects with a given adverse event and the incidence rate, if the same adverse event occurs more than once with the same subject, these events will be taken to be have affected one subject.

SMQ	Range
Suicide/self-injury	Broad search
Hostility/aggression	Broad search

- 8) The number of subjects and incidence rate will be calculated for each study drug dose category (20 mg, 40 mg, 60 mg, 540 mg) at the onset date of adverse event occurring after the initiation of the open-label extension study, by system organ class and preferred term. When calculating the number of subjects and the incidence rate, if the same adverse event occurs in different categories

more than once in the same subject, it will be taken to have occurred with one subject in each of the relevant categories. Adverse drug reactions will be tabulated similarly.

